#### **Trial medication**

The active treatment group (n=25) will be allocated to 1000 IU Vitamin D (Metagenics) + 2.3 g probiotics (Inner Health Kids, Metagenics) daily for 2 months. The control group (n=25) will be allocated to matching placebo drops and powder. Placebo drops and powder, supplied by Metagenics, will be matched in quantity and appearance (odour and colour). Care givers of participating infants will be advised to provide the trial supplements with food in the morning.

Drops and powder can be mixed into the infant formula. If infant is exclusively breastfed, the drops can be given directly into the mouth, the powder can be mixed into water and supplied by spoon.

#### **Compliance & Tolerability**

Compliance and tolerability will be assessed at each visit by Questionnaire and count of remaining trial supplements (drops/powder).

#### **Allocation & blinding**

Active and placebo drops and powder will be packaged and labelled offsite in identical containers by the manufacturing company. Patients, as well as doctors and investigators will be blinded to the group allocation. Coding will remain with the manufacturer until completion of the trial. Blinding success of patients will be evaluated at the end of the trial by questionnaire.

#### **Visits & Assessments**

##### **Visit 1 – week 0 - baseline**

Enrolment, informed consent by GP and chief investigator TN.

Baseline data collection:

- Infant's mother's Vit D supplementation & plasma levels (if known) – during pregnancy and current
- Birth week of gestation, prematurity
- Vaginal, or caesarean birth
- Vit K given to infant at birth?
- Any genetic screening or other test results
- Infant's medication, e.g. PPI for reflux

Assessments: weight, growth, temperature, other symptoms, Carer: Mood Q

Supply of supplements for 4 weeks – and discussion of administration

Supply of diaries: Daily 7pm temperature, infant sleep/cry = infant home diary; Carer sleep diary = Length and Quality of sleep recorded daily)

### **Visit 2 – week 4 – vaccination**

The infant will only be eligible to be vaccinated if its temperature had been less than 38 degrees Celsius in the 4 weeks prior vaccination and since enrolment (at week 0).

Eligibility will be assessed by phone call 1-2 days before the scheduled appointment by NIIM receptionists.

If the infant had run a temperature > 38C in the last 4 weeks, the appointment will be postponed until 4 weeks after the fever.

If eligibility criteria are met, the original appointment will be confirmed.

1) **Assessments:** Weight, growth, temperature, other symptoms, collection of infant home diary and carer sleep diary; Carer: Mood Q; Tolerability & compliance Q

2) **Vaccination:** first immunisation of the Australian standard paediatric immunisation schedule:

a) **Infanrix hexa:** combined Diphtheria-Tetanus-acellular Pertussis (DTPa), hepatitis B, poliovirus and haemophilus influenzae type B vaccine

b) **Prevenar 13:** Pneumococcal polysaccharide conjugate vaccine, 13-valent adsorbed

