## The Vaccination Infant Supplementation (VISS) Study

**Randomised placebo-controlled trial investigating the effect of 8 weeks supplementation with probiotics and vitamin D around routine childhood immunisation on infant's ear temperature, growth, and sleeping pattern in 4-24 month-old infants.**

Infant vaccination numbers in the city of Stonnington and Bundoora have declined over that past decade due to concern over the effect of vaccination. There has been increasing concern that vaccination may adversely affect a child's immune system. However, given the nature of vaccine preventable diseases it is understood that the advantages of disease prevention and vaccination in the community are a priority.

Recent evidence shows that Vitamin D and probiotic supplementation has a beneficial effect on a child's immune system.

This project aims to examine the effect of Vitamin D and probiotics on a child's immune function before and after vaccination in a placebo and treatment group. This project will assess temperature daily for 2 months, pre and post immunisation in a supplemented (Vitamin D and probiotic) and placebo group.

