## **STUDY DESIGN**

Randomised parallel double-blind placebo-controlled trial of 2 months duration investigating the effect of supplementation with vitamin D and probiotics on behavioural and physiological response in infants during routine childhood immunisation.

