***Infanrix hexa and Prevenar 13 Information sheets will be provided by TN to the participating carers.***

➤ Immunisation to be given by same medical doctor and investigator TN for all participants.

3) Supply of supplements for 4 weeks – and discussion of administration

Supply of diary: Daily 7pm temperature, infant sleep/cry

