### **Visit 3 – week 8 – final visit**

1) **Assessments:** Weight, growth, temperature, other symptoms, collection of infant home diary and carer sleep diary; Carer: Mood Q; Tolerability & compliance Q  
& Blinding

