### **Analysis**

Analyses will be performed using SPSS (PASW version 18). Statistical significance will be set at  $p < 0.05$ . Between-group differences will be analysed by ANOVA comparing data after vaccination at 4 weeks (mean of daily data 4-8 weeks incl temperature, sleep/cry, carer sleep; or infant weight/growth data or carer mood data at 8 weeks) to data before vaccination (mean of daily data 0-4 weeks; or at 0 and 4 weeks).

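### Vaccination can be postponed after a fever, but the post-vaccination window, final visit and trial duration stay tied to fixed study weeks

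*Protocol*

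**What the plan says.** - **Visit 2 (Protocol).** Vaccination is nominally at week 4, provided the infant has had no fever in the preceding four weeks and since enrolment. Otherwise "the appointment will be postponed until 4 weeks after the fever". The check is by telephone: "Eligibility will be assessed by phone call 1-2 days before the scheduled appointment". The whole appointment moves, so assessments, diary collection, vaccination and resupply move with it.
- **Analysis.** The *after* data are "mean of daily data 4-8 weeks incl temperature, sleep/cry, carer sleep", or the week-8 value for growth and carer mood. The *before* data are "mean of daily data 0-4 weeks; or at 0 and 4 weeks".
- **Final visit.** "Visit 3 – week 8 – final visit".
- **Duration.** The title describes a trial "investigating the effect of 8 weeks supplementation with probiotics and vitamin D around routine childhood immunisation". Study Design has "Randomised parallel double-blind placebo-controlled trial of 2 months duration". Intervention/Comparison and Trial medication both give two months of daily product.
- **Supply.** Visit 1 issues product for four weeks. Visit 2 does so again ("3) Supply of supplements for 4 weeks") and hands out a fresh diary.

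The contents of the time line and flow chart are not visible in the text available for review.

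**The concern.** The vaccination date varies between infants, but the windows named after it are given in study weeks. For a postponed infant, *after vaccination* and *weeks 4-8* cannot both be true. The visible text does not move the windows, the final visit or the duration when vaccination moves.

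Postponed infants are also picked out after randomisation by their temperature, which is a primary outcome. The protocol's stated purpose is to obtain baseline values and variance for a larger study, so different handling of these infants would give different inputs to that study. This is more than a detail left for an SAP: the protocol itself sets both the postponement rule and the windows, and no later analysis can recover diary days or a visit that were never scheduled.

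**Working it through.** The protocol gives no figure to reproduce here: no fever rate, effect size or standard deviation. The check is calendar arithmetic.

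**Inputs.** Planned vaccination on day 28; fever on day d; vaccination after a fever on day d + 28 (Visit 2). *After* window of days 28 to 56, and final visit on day 56 (Analysis, Visit 3). 25 infants per arm (Intervention/Comparison). I take d = 1 to 26, because day 26 is the last day that a call two days before the visit would catch. Averages assume that fever days are evenly spread over that range and that there is one fever per infant; both are assumptions.

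**Literal (calendar-week) reading**

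- Pre-vaccination share of the *after* window = d/28.
- Days from vaccination to week 8 = 56 − (28 + d) = 28 − d.

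| Fever day d | Vaccination day | Pre-vaccination share of *after* | Days from vaccination to week 8 |
|---|---|---|---|
| 7 | 35 | 7/28 = 25% | 21 |
| 14 | 42 | 14/28 = 50% | 14 |
| 21 | 49 | 21/28 = 75% | 7 |
| 26 | 54 | 26/28 = 93% | 2 |

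Mean d = 351/26 = 13.5, so the mean share is 13.5/28 = 48% and the mean follow-up is 14.5 days instead of 28.

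**Weight in the arm.** An arm has 25 × 28 = 700 *after* infant-days. One postponed infant misplaces on average 13.5/700 = 1.9% of them (range 1/700 = 0.1% to 26/700 = 3.7%).

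**Temperature.** If a vaccination response lasts L days (assumption), the part still inside the window is min(L, 28 − d)/L. Averaged over d = 1 to 26:

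| L (days) | Share kept |
|---|---|
| 3 | 25.667/26 = 99% |
| 7 | 23.857/26 = 92% |
| 14 | 20.429/26 = 79% |
| 28 | 14.5/28 = 52% |

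**Growth.** This needs no assumption about response length. The Visit 2 measurement moves with the appointment. A fever on day 14 gives 42 days before vaccination and 14 after, instead of 28 and 28.

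**Nominal-week reading** (week 8 means four weeks after vaccination)

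- Visit 3 falls on day 56 + d, that is day 57 to 82, past the stated 8 weeks.
- *Before* could be 28 days or 28 + d = 29 to 54 days; the text does not say which.

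**The case against.** The strongest reply is that the protocol's operations already imply the nominal reading. All of Visit 2 moves, the diaries are split at that visit, and four weeks of product and a new diary are issued there. On the literal reading, an infant vaccinated on day 54 would receive four weeks of product and be closed out two days later. The Analysis section also names its contrast by the event, before and after vaccination, so the week numbers may only describe the unpostponed schedule. The time line and flow chart, where visit spacing might be shown, are not visible.

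Much of this stands. Four weeks after vaccination is probably what is intended, and the 25% to 93% figures hold only if the weeks are taken literally. But the intention is not written down, it runs past the stated duration, and it leaves the *before* window open.

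A reader might infer three stronger things, none of which the documents support:

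- **The result will be materially diluted or power lost.** This needs a fever rate, an effect size and a lasting response, and the protocol gives none of them. It is a pilot without a power claim.
- **Infants will go without supplement before a postponed vaccination.** A 28-day supply would leave at most d uncovered days, but that assumes no overage. The listed vitamin D product is a 360-day bottle, and the powder pack size is not shown.
- **The arms will be biased against each other.** Postponement could differ by arm because its trigger is a post-randomisation temperature, but nothing shows that it will.

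**Conclusion.** The point holds as an internal conflict. The postponement rule makes the vaccination date variable, while the Analysis section, the final visit and the stated duration treat it as week 4. Followed as written, the *after* value of a postponed infant includes d unvaccinated days out of 28, and week-8 growth and mood have only 28 − d days of post-vaccination follow-up.

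The effect on a short temperature reaction is small. It is larger for growth, carer mood or any shift lasting weeks: a 28-day shift would be about halved in that infant. The overall effect cannot be sized, because the number of postponed infants is unknown. Severity is minor to moderate.

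**What to change.** 1. **Analysis:** define *after* as the 28 days from each infant's actual vaccination.
2. **Visit 3:** set the final visit and the end of the diary at four weeks after actual vaccination.
3. **Study Design, Intervention/Comparison, Trial medication:** let the two months extend to that date for postponed infants, and continue product and diary through any delay.
4. **Before window:** prespecify one 28-day window that ends no later than vaccination, and apply it to all infants. The first 28 days from enrolment and the last 28 days before vaccination are both defensible. They coincide for an infant vaccinated on day 28. For a postponed infant, the first contains the triggering fever and the second does not. The choice is the sponsor's.
5. Analyse postponed infants in their randomised arm.

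The cost is a few sentences of wording plus extra product and diary pages. The downside is that postponed infants stay on product and in the study up to about four weeks longer per fever, have had more than 28 days of product at vaccination, and have a growth interval of 57 to 82 days instead of 56. A second fever would lengthen this further.

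### A fever postpones vaccination, but the before and after windows, Visit 3 and the four-week first supply are not adjusted to the new date

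*Protocol*

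**What the plan says.** Under Visit 2, vaccination requires a temperature "less than 38 degrees Celsius in the 4 weeks prior vaccination and since enrolment (at week 0"). The infant is screened by telephone one or two days ahead. "If the infant had run a temperature > 38C in the last 4 weeks", then "the appointment will be postponed until 4 weeks after the fever". Vaccination, the exchange of diaries and the second four-week supply all belong to that appointment.

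The Analysis section describes the contrast as "comparing data after vaccination at 4 weeks (mean of daily data 4-8 weeks incl temperature" and other daily measures, set against "data before vaccination (mean of daily data 0-4 weeks; or at 0 and 4 weeks"). It does not mention postponed infants.

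Three other places assume the standard calendar:

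- Visit 1 provides "Supply of supplements for 4 weeks".
- The last visit is headed "Visit 3 – week 8 – final visit".
- The Study Design section describes a "Randomised parallel double-blind placebo-controlled trial of 2 months duration".

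The outcome table lists ear temperature, measured daily, and weight and growth, measured at weeks 0, 4 and 8, as primary.

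**The concern.** The eligibility wording treats the four weeks before vaccination and the time since enrolment as the same interval. They coincide only for an infant vaccinated on schedule. For a postponed infant they separate, and the protocol does not say which clock governs the analysis windows, Visit 3 or the first supply. Either choice conflicts with something it states.

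- **Weeks counted from enrolment.** The after-vaccination mean includes days on which the infant had not been vaccinated. A vaccination effect spread over the following weeks is diluted in that infant.
- **Weeks following the actual Visit 2.** The before period is longer than weeks 0-4, Visit 3 falls later than two months, and the infant may have no powder in the days before vaccination. Supplementation around vaccination is the exposure that the trial studies.

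Postponement depends on a temperature taken after randomisation while the infant is on supplement or placebo. If the supplement changes the frequency of fevers, more infants are affected in one arm than in the other. The pilot's stated purpose, to obtain baseline values and variance for a larger study, suffers as well when pre- and post-vaccination days are mixed.

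**Working it through.** The protocol gives no figure to reproduce, so the check is calendar arithmetic.

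**Inputs.** Enrolment is day 0, week 4 is day 28 and week 8 is day 56 (visit headings). There is one temperature reading a day, at 7 pm (Tympanic ear temperature section). The call is on day 26 or 27 (Visit 2). Vaccination after a single fever on day d is on day d + 28 (Visit 2). The after window in study weeks is days 28-55, which is 28 readings (Analysis).

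**Range of d.** The latest fever that the call can detect is on day 25 to 27, depending on the day of the call and whether that day's reading counts. I use d = 1 to 26, so vaccination falls on days 29-54. The upper end could be 53 or 55. A second fever during the wait moves it further: a fever on day 53 gives day 81.

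**Weeks counted from enrolment.** Readings in the after window that precede vaccination are days 28 to d + 27, so there are d of them, a share of d/28. Readings left after vaccination number 28 − d.

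**Weeks following the actual Visit 2.** If exactly 28 days of product are dispensed, the gap is (d + 28) − 28 = d days. The before period has 28 + d readings. Visit 3 falls on day d + 56.

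| Fever day d | Vaccination day | Pre-vaccination readings in after window | Readings left after vaccination | Possible supply gap (days) | Visit 3 if re-anchored |
|---|---|---|---|---|---|
| 1 | 29 | 1 (3.6%) | 27 | 1 | day 57 |
| 7 | 35 | 7 (25%) | 21 | 7 | day 63 |
| 14 | 42 | 14 (50%) | 14 | 14 | day 70 |
| 21 | 49 | 21 (75%) | 7 | 21 | day 77 |
| 26 | 54 | 26 (92.9%) | 2 | 26 | day 82 |

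If Visit 3 stays at day 56, a day-26 fever also leaves the second and third weight measurements 56 − 54 = 2 days apart.

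**Illustration across the trial, under assumptions not in the protocol.** Let d be equally likely from 1 to 26 (mean 13.5), with weeks counted from enrolment and a constant shift throughout the four weeks after vaccination. A postponed infant loses on average 13.5/28 = 48.2% of that shift. If a proportion q is postponed, the mean shift retained is 1 − 0.482q:

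- q = 10%: 95%
- q = 20%: 90%
- q = 30%: 86%
- q = 50%: 76%

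If 10% were postponed in one arm and 30% in the other, 0.10 × 48.2% = 4.8% of after readings in the first and 0.30 × 48.2% = 14.5% in the second would precede vaccination. Two arms with the same true shift would then appear to differ by 14.5% − 4.8%, about 10% of it.

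**The case against.** The best reply is that week 4 and week 8 are labels for visits. The visit headed week 4 may itself be postponed, the Analysis section speaks of data before and after vaccination with the week numbers in parentheses, and the diaries are exchanged at Visit 2, so the records divide at the actual vaccination. This reading is plausible and may be the intended one. But the protocol never states it, and the Analysis section places vaccination at 4 weeks. Even on this reading, the first supply and the stated duration do not fit a postponed infant. An analysis plan could settle the windows. Resupply, diary continuation and the date of Visit 3 are matters of conduct that belong in the protocol.

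Several stronger inferences are not supported:

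- *All supply is fixed to the calendar.* It is not. The second supply is issued at Visit 2 and moves with it, and none is issued at Visit 3. Only the quantity given at Visit 1 is fixed.
- *Postponed infants will be without product.* This cannot be established. The vitamin D bottle is listed as 360 days, no powder pack size is given, and leftovers are counted at each visit. A gap is possible, chiefly for the powder.
- *The comparison between arms is shown to be biased.* It is not. Equal postponement in both arms dilutes a common effect but does not favour either arm. Bias needs unequal postponement, which is possible but not documented.
- *The fever should be kept out of the before mean.* On-schedule infants are fever-free there by rule and postponed infants are not. But removing those readings would select the pre-vaccination data on a post-randomisation outcome that the supplement may change.
- *A short reaction would be missed.* For a single fever up to day 26, at least two post-vaccination readings remain by week 8, so a reaction of one or two days still falls inside the window.

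**Conclusion.** The point stands as a conflict in the current text: the vaccination date can move, and the windows, the final visit and the first supply are written as though it cannot. For an infant postponed once, either 1 to 26 of the 28 after-vaccination readings precede vaccination, or the first supply can fall short by up to the same number of days. Which of these applies depends on how weeks are counted, which the protocol leaves open. The second also assumes that no more than 28 days of product are dispensed.

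Day 54 is not a firm limit, since it assumes one fever found at the call. The effect on the trial as a whole is unknown because the protocol gives no fever rate. The percentages across the trial are illustrations, not estimates. This is a moderate point that should be corrected: it affects a primary outcome in infants selected by a post-randomisation event, and the correction is cheap.

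**What to change.** In the Analysis section, define the after period as the 28 daily readings starting on the actual vaccination day, and the before period as all daily readings from enrolment to the day before vaccination. Apply both identically in the two arms and do not drop fever readings. For an infant vaccinated on day 28 this gives days 28-55 and days 0-27, so nothing changes. For an infant postponed once, the before mean rests on 29 to 54 readings.

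In the Visit 1 to Visit 3 sections, state that a postponed infant continues supplements and diary, receives enough product to reach the postponed Visit 2, and has Visit 3 four weeks after the actual vaccination. Report pre-vaccination fevers and postponements by arm.

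The cost is an amendment to the wording and up to about four extra weeks of supplement and diary for each infant postponed once. Those infants also have a longer exposure before vaccination, and the report should say so. The scheduled number of visits, the randomisation and the sample size are unchanged.

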### AUSTRALIAN IMMUNISATION SCHEDULE 

The current Australian routine immunisation schedule is:

|           |   |
|-----------|---|
| Birth     | 

• Hepatitis B (hepB)a

  |
| 2 months  | 

• Infanrix hexa: Hepatitis B, diphtheria, tetanus, acellular pertussis (whooping cough), Haemophilus influenzae type b, inactivated poliomyelitis (polio) (hepB-DTPa-Hib-IPV)

• Prevenar 13: Pneumococcal conjugate (13vPCV) • Rotavirus

 |
| 4 months  | 

• Infanrix hexa: Hepatitis B, diphtheria, tetanus, acellular pertussis (whooping cough), Haemophilus influenzae type b, inactivated poliomyelitis (polio) (hepB-DTPa-Hib-IPV)

• Prevenar 13: Pneumococcal conjugate (13vPCV) • Rotavirus

 |
| 6 months  | 

• Infanrix hexa: Hepatitis B, diphtheria, tetanus, acellular pertussis (whooping cough), Haemophilus influenzae type b, inactivated poliomyelitis (polio) (hepB-DTPa-Hib-IPV)

• Prevenar 13: Pneumococcal conjugate (13vPCV)

             |
| 12 months | 

• Haemophilus influenzae type b and meningococcal C (Hib-MenC) • Measles, mumps and rubella (MMR)

  |
| 18 months | 

• Diphtheria, tetanus, pertussis (whooping cough) (DTPa)

• Measles, mumps, rubella and varicella (chickenpox) (MMRV)

  |
| 4 years   | 

• Diphtheria, tetanus, acellular pertussis (whooping cough) and inactivated poliomyelitis (polio) (DTPa-IPV)

  |

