### **Participants**

#### **Inclusion criteria**

- Group 1 (preferred): Infants who have not yet been immunised (age range: 4-24 months).
- Group 2: Infants who have been immunised (age range: 4-24 months).
- Parents have agreed to have their child immunised.
- Normal infant growth as per WHO growth charts:  
<http://www.education.vic.gov.au/Documents/childhood/parents/mch/mchgrowthboy24mths.pdf>
- <http://www.education.vic.gov.au/Documents/childhood/parents/mch/mchgrowthgirl24mths.pdf>
- No tympanic temperature > 38 degrees Celsius in the preceding 4 weeks prior to immunisation
- Infants currently breastfed (e.g. exclusively or breast and formula fed)
- Infants currently not taking supplements (Vitamin D and/or probiotics)
- Infants who will remain in the same routine with primary carers for the 2 month study period
- Willing to contribute 50% (\$30) of the cost price for ear thermometer

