#### **Enrolment & randomisation**

The doctor and chief investigator TN will meet patients at the NIIM clinic to confirm eligibility and to collect the infant's care givers informed consent. Two groups will be recruited into this pilot study, group 1: vaccination-naïve (not yet immunised) infants 4-24 months into the study, and group 2: vaccinated infants 4-24 months.

Eligible infants will be enrolled and randomised. A computer-generated permuted block randomisation schedule prepared by a researcher not involved in patient recruitment and data collection will be used to allocate patients to the active or placebo groups.

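### Visit 2 states one vaccination with no branch for already immunised infants, and for those due a 12- or 18-month dose the named products contradict the protocol's own schedule

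*Protocol*

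**What the plan says.** All references are to the protocol.

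- **Who is enrolled.** The section *Enrolment & randomisation* states that "Two groups will be recruited into this pilot study": vaccine-naive infants (group 1) and "group 2: vaccinated infants 4-24 months". *Inclusion criteria* lists the same two groups, marks group 1 as preferred, and requires for entry that "Parents have agreed to have their child immunised".
- **What is given.** *Visit 2 – week 4 – vaccination* specifies one regimen, the "first immunisation of the Australian standard paediatric immunisation schedule", itemised as Infanrix hexa and Prevenar 13. It does not distinguish the groups.
- **What goes with it.** The text that follows says "Infanrix hexa and Prevenar 13 Information sheets will be provided by" the investigator, and that one doctor immunises "for all participants". No sheet for any other vaccine is mentioned.
- **What the schedule lists.** *Australian Immunisation Schedule* has Infanrix hexa and Prevenar 13 at 2, 4 and 6 months, Hib-MenC and MMR at 12 months, and DTPa and MMRV at 18 months. Before these comes a hepatitis B dose at birth.
- **How the vaccination is used.** *Analysis* compares the four weeks after the Visit 2 vaccination with the period before it.

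**The concern.** The Visit 2 text fits a vaccine-naive infant, but the trial also randomises infants who have been vaccinated. If the text is followed literally, some of those infants would receive products that the protocol's own schedule does not list at their age, and the only sheets it mentions would cover those products.

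There is also a consequence for interpretation. The Visit 2 vaccination separates the before and after periods for temperature, sleep and crying, and growth. If the protocol misdescribes it for part of the sample, a reader cannot tell from the protocol which vaccine or which dose those results follow. That matters for a pilot whose stated purpose, in *Sample size & Justification*, is to supply baseline values and variance for a larger trial.

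**Working it through.** There is no figure in the protocol to reproduce. The check is one of consistency between eligibility, the visit procedure and the schedule.

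**Step 1. Does the Visit 2 regimen reach group 2?** Both groups are recruited and randomised. Visit 2 has no branch by group, and the sentence about who vaccinates assumes that every participant is immunised. No other visible section gives group 2 a different vaccination. So the stated regimen applies to group 2 by default.

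**Step 2. Does the regimen fit what a group 2 infant is due?**

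| Dose due at Visit 2 | Schedule lists | Named products fit? | Is it a first dose? |
|---|---|---|---|
| 4-month | Infanrix hexa, Prevenar 13 (with rotavirus) | Yes, both are listed | No, if the 2-month dose was given |
| 6-month | Infanrix hexa, Prevenar 13 | Yes | No, if earlier doses were given |
| 12-month | Hib-MenC, MMR | **No** | No |
| 18-month | DTPa, MMRV | **No** | No |

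The last two rows are the substantive conflict. Reading *first* loosely could repair the last column but not the product list.

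**Step 3. Can those two rows occur within the enrolment ages?** Visit 2 is four weeks after enrolment: 28 / 30.4 = 0.92 months. An infant vaccinated on time reaches the 12-month dose at Visit 2 if enrolled at 12 − 0.92 = 11.1 months, and the 18-month dose if enrolled at 18 − 0.92 = 17.1 months. Both ages lie inside the 4 to 24 month range, so the conflict can arise for ordinary, on-schedule infants.

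**Step 4. How many infants are affected?** This cannot be computed. The total is 50 (25 per arm), but neither the split between groups 1 and 2 nor the ages within group 2 are given.

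**Step 5. Would the data show what was given?** The baseline items listed under *Assessments* and *Visit 1* do not include doses already received. The assessments listed for Visit 2 do not include the product or dose number administered. From the visible text, the vaccination a group 2 infant received could not be reconstructed.

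**The case against.** **The word *first* may be right for some of group 2.** The schedule starts with hepatitis B at birth, so *first immunisation* in the Visit 2 text must already mean the 2-month item. The protocol does not define *immunised*. An infant who has had only the birth dose might be placed in group 2, and the Visit 2 text would then be right in wording and products. This stands. A reader might infer that the text is wrong for every group 2 infant; the documents do not support that. The product conflict concerns up-to-date infants due a 12- or 18-month dose. Infants behind schedule may still be due the named products.

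**The vaccinating doctor would follow the national schedule.** Visit 2 refers to that schedule, and *Study design* speaks of routine childhood immunisation. So the text is better read as contradicting itself than as a deliberate order to depart from the schedule. That is fair, but following the schedule would then mean departing from the products the protocol names.

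**The phrase "for all participants" mainly fixes who vaccinates.** Agreed: it does not say that everyone gets the same products. The point does not depend on it, because Visit 2 itself names only one regimen.

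**Relevant material may be out of view.** The timeline and flow chart are not shown and the consent pages were removed, so a group 2 branch or further vaccine information may exist. For that reason it cannot be said that carers would receive no other information. A correct figure elsewhere would still disagree with the Visit 2 text.

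**This is a small pilot, and handling of the groups in the analysis may sit in the SAP.** True for the analysis, so no analysis change is asked for. Which vaccine is given at a visit is a protocol procedure.

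**Conclusion.** The point holds in a limited form. The Visit 2 text gives a single regimen. For group 2 infants who are up to date and due a 12- or 18-month dose, its products contradict the protocol's own schedule. For those due a 4- or 6-month dose, only the description as a first dose is wrong. Group 1 is not in question. The conclusion rests on the visible text and takes *up to date* to mean vaccinated at the ages in the printed schedule.

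Two stronger inferences should be resisted:

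- **Bias in the randomised comparison.** A reader might infer that mixed vaccines distort the active-placebo contrast. Infants are randomised to arm, and nothing in the protocol ties product or dose number to arm. Any effect on variability would need assumed inputs and may be nil.
- **Most infants affected.** Much of the enrolment age range lies beyond 6 months, but a share of an age range is not a share of infants. The range also covers group 1, infants behind schedule, and long intervals in which an up-to-date infant is due nothing.

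The number affected is therefore unknown and could be small. The error is still worth correcting, because it concerns what is injected and what event the results refer to, and correction is cheap.

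**What to change.** 1. **Amend *Visit 2 – week 4 – vaccination*.** Group 1 receives the first dose of Infanrix hexa and Prevenar 13. Group 2 receives the next dose due for age and previous doses under the schedule printed in the protocol.
2. **Match the information sheets** to the products each infant will receive.
3. **Record product and dose number at Visit 2**, so that the vaccination dividing the before and after periods in *Analysis* is correctly described for each infant.

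The cost is one or two protocol sentences, the matching sheets and one form field. Sample size, randomisation and the planned ANOVA stay as they are. Correcting this error does not require closing entry to group 2 or restricting it by age; that would be a separate eligibility decision for the sponsor.
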